10.2 Analysis of secondary objectives

10.2.1 Efficacy (secondary)

Secondary endpoints at 6 months, 1, 2 and 3 years will include: graft survival and patient survival/death at 2 and 3 years, rate and grade of acute cellular rejection, rate of acute antibody mediated rejection, rate of new donor specific antibody formation, estimated CrCl by MDRD, lipid control as determined by requirement for anti-lipid medications and average levels with and without medications, ability to maintain initial immunosuppressive medications and reason for switch if required, wound complications as determined by need for wound packing, infection treatment with antibiotics, presence of hernia on exam and requirement for hernia repair, as well as presence of symptomatic lymphocele, and New Onset Diabetes After Transplant as determined by need for new oral or sustained Insulin medication.

Statistical analysis will be performed on SPSS or STATA software with dichotomous variables evaluated by Chi-Squared analysis, continuous variables by Student's T-Test, non-parametric outcomes will be assessed by Wilcoxon rank sum test (Mann-Whitney U test). Kaplan-Meier survival curves with log rank tests will be used to determine a difference in graft and patient survival over time.

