- Results of 12 month surveillance biopsies
- Lipid panels and use of lipid lowering medications at 1 year after transplant
- Incidence of MI and CHF at 1 and 3 years after transplant

- Incidence of wound infection at 1 year after transplantation
- Incidence of lymphocele at 1 year after transplantation
- Plasma concentrations of S-adenosyl homocysteine (SAH) and S-adenosyl methionine (SAM) Plasma concentrations of endothelial dysfunction markers (symmetric and asymmetric dimethyl arginine (SDMA, ADMA), L-arginine, L-citrulline, L-ornithine, cysteine, and homocysteine over the observation period
- Plasma concentrations of bioactive lipids (HODEs, HEPEs, HETEs, and prostaglandins) over the observation period
- Plasma protein patterns

Data analysis: The incidence of graft loss, patient death, and acute rejection will be compared by chi squared analyses. Patient and graft Kaplan-Meier survival curves will be compared by log rank test. We hypothesize there will be no statistically significant difference between the treatment arms. As this is a pilot study, it was not statistically powered to detect subtle differences in outcome. All continuous variables such as serum creatinine, cGFR, serum lipids, WBC, platelets, etcetera will be compared by student's t test. Any other dichotomous variables will be compared by chi squared analysis.

1 Background

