3.2 Secondary objectives

Secondary outcomes would include factors involved with adverse events and tolerability and would include: renal graft survival (non-death censored) and biopsy proven acute rejection at 6 months, 2 and 3 years, as well as the number and grade of acute rejection episodes and responsiveness to treatment, serum creatinine and estimated GFR, results of renal biopsies at 12 months post-transplant to look for histological evidence of graft injury, early and late wound complications, infections including CMV, EBV and BK infections as monitored by serum PCR testing, lipid panel testing, particularly triglycerides, cardiac events such as acute myocardial infarctions or Congestive Heart Failure episodes, and tolerability of the Neoral and mTOR combination as determined by the patients who required conversion off of the intended randomized drug combination, with attempt to document why the patient did not tolerate the drug combination. All objectives are exploratory in nature as this is a pilot study.

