10.1.2 Statistical hypothesis, model, and method of analysis

The primary endpoint will be a composite endpoint of graft survival (non-death censored) and biopsy proven acute rejection at 1 year.

Secondary endpoints at 6 months, 1, 2 and 3 years will include: graft survival and patient survival/death at 2 and 3 years, rate and grade of acute cellular rejection, rate of acute antibody mediated rejection, rate of new donor specific antibody formation, estimated CrCl by MDRD, lipid control as determined by requirement for anti-lipid medications and average levels with and without medications, ability to maintain initial immunosuppressive medications and reason for switch if required, wound complications as determined by need for wound packing, infection treatment with antibiotics, presence of hernia on exam and requirement for hernia repair, as well as presence of symptomatic lymphocele, and New Onset Diabetes After Transplant as determined by need for new oral or sustained Insulin medication.

Statistical analysis will be performed on SPSS or STATA software with dichotomous variables evaluated by Chi-Squared analysis, continuous variables by Student's T-Test, non-parametric outcomes will be assessed by Wilcoxon rank sum test (Mann-Whitney U test). Kaplan-Meier survival curves with log rank tests will be used to determine a difference in graft and patient survival over time.

Safety data will include patient and graft survival, biopsy proven acute rejection, and hospital admissions.

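### The lipid endpoint appears to average levels separately by lipid-lowering use, which can follow from the assigned drug; the plan should name the all-patient, baseline-adjusted comparison as the main one

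*Combined protocol and SAP*

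**What the plan says.** Section 3.2 lists "lipid panel testing, particularly triglycerides" among the secondary outcomes. Sections 10.1.2 and 10.2.1, in identical wording, define the endpoint as "lipid control as determined by requirement for anti-lipid medications and average levels with and without medications". The sentence opens with "Secondary endpoints at 6 months, 1, 2 and 3 years will include", so medication use and levels are both post-randomisation measurements. The next paragraph assigns tests by type of variable: "dichotomous variables evaluated by Chi-Squared analysis" and "continuous variables by Student's T-Test".

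The synopsis describes lipids differently. Its list of other assessments has "Lipid panels and use of lipid lowering medications at 1 year after transplant". Its data-analysis paragraph says "All continuous variables such as serum creatinine, cGFR, serum lipids, WBC, platelets, etcetera will be compared by student's t test", with no division by medication.

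Randomisation is stratified by donor type and by primary versus repeat transplant (section 6.3), not by lipid medication. The trial is open-label (section 6.4). Patients already on lipid-lowering therapy may enter if they are within the lipid limits (section 5.2). Table 7-1 schedules a lipid panel at screening and at months 6, 12, 24 and 36. No section adjusts lipids for baseline or says how lipid medication started after randomisation is handled.

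**The concern.** Need for lipid-lowering medication is listed as an outcome, and the same sentence appears to use it to sort patients before levels are averaged. Such medication is generally started because lipids are high, and in an open-label trial prescribing may also depend on the known drug. If one drug raises lipids more, its arm sends more patients into the medicated group, including some only just above the prescribing level, and keeps only its lower patients in the unmedicated group. Within each group the arms no longer differ by randomisation alone.

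The background section says the trial's secondary interest is the Zortress side-effect profile and any favourable difference from Rapamune, and triglycerides are singled out. A lipid comparison that tends to understate a difference works against that aim.

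**Working it through.** **Inputs from the documents.** 60 patients at 2:1 gives 60 × 2/3 = 40 Zortress and 60 × 1/3 = 20 sirolimus. The plan states no lipid effect, SD, significance level or power, so it has no figure of its own to reproduce. Everything below on size is assumed (two-sided 5% tests throughout). Only the direction is an argument about the design.

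**Step 1: the mechanism by hand.** Let the untreated level be normal with SD 1, mean 0 on Zortress and 0.5 on sirolimus. Suppose medication starts above 0.5 and lowers the level by a constant, which cancels among users.

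- Users: the Zortress mean is φ(0.5)/[1 − Φ(0.5)] = 0.352/0.309 = 1.14. The sirolimus mean is 0.5 + φ(0)/0.5 = 0.5 + 0.80 = 1.30. The difference is **0.16**.
- Non-users: the Zortress mean is −0.352/0.691 = −0.51. The sirolimus mean is 0.5 − 0.80 = −0.30. The difference is **0.21**.
- All patients: 31% v 50% are medicated. The difference is 0.5 − drop × (0.50 − 0.31), which is **0.40** for a drop of 0.5 and **0.31** for a drop of 1.0.

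A true 0.5 SD thus shows as 0.16 and 0.21 in the split groups, and as 0.31 to 0.40 unsplit.

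**Step 2: range over prescribing rules.** I simulated 36 scenarios: true difference 0.5 or 1.0 SD; threshold 0, 0.5 or 1.0; drop 0.5 or 1.0; prescribing noise 0, 0.5 or 1.0.

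| True difference (SD) | Users | Non-users | All patients |
|---|---|---|---|
| 0.5 | 0.11–0.35 | 0.16–0.37 | 0.31–0.44 |
| 1.0 | 0.27–0.73 | 0.27–0.73 | 0.62–0.87 |

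The split groups understated the true difference in all 36.

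**Step 3: precision at 40 v 20.** The standard error for all patients is √(1/40 + 1/20) = 0.274 SD, so the difference detectable with 80% power is (1.96 + 0.84) × 0.274 = 0.77 SD. With threshold and noise both 0.5 and a true difference of 0.5 SD, about 13 v 10 patients are medicated. The standard error is then √(1/13 + 1/10) = 0.421, or 1.5 times as large for the same SD (selection narrows the SD, which offsets part of this). Simulated power in that setting:

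| True difference (SD) | Users | Non-users | All patients | Medication use (chi-squared) |
|---|---|---|---|---|
| 0.5 | 12% | 14–15% | 34–42% | 26–27% |
| 1.0 | 39% | 29–30% | 88–95% | 73–74% |

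With no true difference, rejection rates for the level comparisons stayed at 4.4–5.3%.

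**Step 4: a triglyceride example.** Assume lognormal untreated levels with means 180 (Zortress) v 210 (Rapamune) mg/dl and SD 70. The probability of medication is 1/[1 + exp(−(level − 200)/s)], and medication lowers the level by 30%. A value of s = 15 is close to a sharp cut-off; s = 50 is a gradual one.

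| Difference, mg/dl (untreated: 30) | s = 15 | s = 50 |
|---|---|---|
| Users | 4.7 | 14.0 |
| Non-users | 16.9 | about 24 |
| All patients, observed level | 16.3 | about 19 |

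At s = 15, medication use is 34% v 50%, and t-test power at 40 v 20 is about 6% (users), 23% (non-users) and 29% (all).

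**The case against.** Much of the remedy is already planned. The synopsis t-test of serum lipids is unsplit, and medication use comes first in the endpoint and falls under chi-squared. Both are randomised comparisons if made on all patients, and either could show a difference. This stands. A reader might infer that the plan has no valid lipid comparison, and that would be wrong. What is missing is a statement of which analysis leads, and any baseline adjustment.

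A reader might also infer that the plan commits to between-arm t-tests within each medication group. It does not say so. The t-test sentence covers continuous variables generally, and "average levels with and without medications" could mean a descriptive report, averages before and after starting therapy, or a split by use at entry. The last would be unobjectionable because use at entry precedes randomisation. Separate averages by current use is the natural reading, but it remains a reading.

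The size depends on the assumed prescribing rule: the users' figure moves from about 5 to 14 mg/dl as the threshold softens. Nor should 30 mg/dl be taken as what an all-patient analysis would recover. In the triglyceride example that analysis shows 16 to 19, no more than among non-users, because more patients are treated in the arm with higher levels. Its advantage is validity and number of patients, not restoration of the untreated difference.

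Finally, the plan calls all its objectives exploratory and says it is not powered (sections 3.2 and 10.3), and no stopping provision uses lipids. That limits the priority. It does not make the split comparison interpretable.

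**Conclusion.** The point holds as a matter of analysis choice and clarity. On its natural reading the lipid endpoint divides patients by something the assigned drug can change. Arm differences within those groups are not randomised, rest on fewer patients and understated the true difference in every scenario tried. The synopsis offers a sounder comparison, but the documents do not rank the two and neither uses the baseline panel.

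In the triglyceride example, 30 mg/dl appears as about 5 to 14 among users, 17 to 24 among non-users and 16 to 19 overall. Those figures rest wholly on assumed means, SD, threshold, sharpness and treatment effect.

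Two stronger conclusions are not supported. The first is that a drug effect would necessarily be hidden: medication use would also differ (34% v 50% in the example) and is itself an endpoint. The second is that the split produces false positives: in the model with no true difference, error rates stayed near 5%. The risk is understatement in one secondary endpoint of an exploratory pilot. The priority is low to moderate.

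**What to change.** In sections 10.1.2 and 10.2.1, and to match in the synopsis:

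1. Name as the main lipid analysis the comparison of levels at each time point in all randomised patients by assigned arm, regardless of lipid-lowering treatment, adjusted for the screening value (for example by analysis of covariance).
2. Report the proportion on lipid-lowering medication in each arm beside it, with the planned chi-squared test, so that dilution by treatment can be judged.
3. Keep the averages with and without medication as a descriptive table without tests, and say whether the division is by use at entry or at the visit.

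The cost is a few sentences. The screening and follow-up panels are already in Table 7-1 and medication use is already an endpoint, so no extra patients, visits or samples are needed.

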The patient population will be all adults (18-75 years of age) who receive a living donor or deceased donor renal transplant as a first or subsequent renal transplant procedure only (no extra-renal organ transplant recipients). We will invite any patient who would normally be considered for our current Sirolimus®/ Neoral® protocol with Thymoglobulin® and steroid induction to consent for this pilot study and then undergo randomization post-operatively if the transplant surgeon anticipates normal early graft function. If there were significant concerns for prolonged graft dysfunction, then the patients will not be invited into the pilot study. Invited patients would include anyone currently not on steroids prior to transplantation, and those with no known intolerance to any of the drugs mentioned. Patients must also be willing to perform the expectations of the study protocol reliably.

This will be a single center pilot study performed at The Ohio State University Comprehensive Transplant Center. Our center performs approximately 100 to 110 living donor and 90 to 100 deceased donor renal transplants per year. If we assume that at least 150 patients per year qualify for the study, then a conservative estimate of 75 enrolled patients a year is possible. We would propose to enroll a total of 60 patients over 12 months, and then follow these patients for a complete 3 years. We will randomize 2:1 Zortress to Sirolimus using a random number generator.

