5.2 Exclusion criteria

- Exclusion Criteria at the time of enrollment:
 - Total cholesterol > 300 mg/dl or triglycerides > 400 mg/dl despite lipid lowering therapy
 - Pre-existing bone marrow suppression (WBC < 3000, platelets < 100,000)
 - Positive crossmatch or ABO incompatible

- Pregnant or nursing (lactating) women, where pregnancy is defined as the state of a female after conception and until the termination of gestation, confirmed by a positive serum human chorionic gonadotrophin laboratory test (>5 mIU/mL)
- Women of child-bearing potential, defined as all women physiologically capable of becoming pregnant, including women whose career, lifestyle, or sexual orientation precludes intercourse with a male partner and women whose partners have been sterilized by vasectomy or other means, UNLESS they are using two birth control methods. The two methods can be a double barrier method or a barrier method plus a hormonal method.
 - Adequate barrier methods of contraception include: diaphragm, condom (by the partner), intrauterine device (copper or hormonal), sponge or spermicide. Hormonal contraceptives include any marketed contraceptive agent that includes an estrogen and/or a progestational agent.
 - Reliable contraception should be maintained throughout the study and for 12 weeks after study drug discontinuation.
 - Women are considered post-menopausal and not of child bearing potential if they have had 12 months of natural (spontaneous) amenorrhea with an appropriate clinical profile (e.g. age appropriate, history of vasomotor symptoms) or six months of spontaneous amenorrhea with serum FSH levels > 40 mIU/mL and estradiol < 20 pg/mL] or have had surgical bilateral oophorectomy (with or without hysterectomy) at least six weeks ago. In the case of oophorectomy alone, only when the reproductive status of the woman has been confirmed by follow up hormone level assessment is she considered not of child bearing potential.
- Active infection (HBV, HIV)
- Malignancy (except for adequately treated squamous or basal cell skin carcinoma) unless patient has written clearance from an Oncologist or if patient has had no malignancy for at least 2 years prior to the transplant
- Allergy or intolerance to sirolimus, everolimus, cyclosporine, or ATG

6 Treatment

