6.3 Treatment assignment

Randomization will be stratified by type of donor kidney received (living or deceased donor kidney) and primary versus retransplant recipient. Randomization will be performed using a random number generator.

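### The lipid-medication outcome counts patients already treated before transplant, so any difference between arms in new need for treatment is diluted by an amount the plan cannot yet gauge

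*Combined protocol and SAP*

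**What the plan says.** Sections 10.1.2 and 10.2.1 list, among the secondary endpoints at 6 months and 1, 2 and 3 years, "lipid control as determined by requirement for anti-lipid medications and average levels with and without medications". The synopsis, under other assessments, has "Lipid panels and use of lipid lowering medications at 1 year after transplant". None of the three places mentions treatment status before transplant.

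The lipid exclusion in section 5.2 (and the synopsis) is "Total cholesterol > 300 mg/dl or triglycerides > 400 mg/dl despite lipid lowering therapy". It removes patients who stay above the limits on treatment. Treated patients below the limits can enter.

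The same sentence of 10.2.1 handles diabetes differently: "New Onset Diabetes After Transplant as determined by need for new oral or sustained Insulin medication". That outcome is restricted to new treatment, and the donor-specific antibody outcome in the sentence is likewise restricted to new formation.

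For yes/no outcomes the method is "dichotomous variables evaluated by Chi-Squared analysis", with no adjustment for baseline. Section 6.3 says "Randomization will be stratified by type of donor kidney received (living or deceased donor kidney) and primary versus retransplant recipient", so lipid therapy at entry is not balanced by design. Table 7-1 schedules a screening lipid panel and a medical history, but it has no row for concomitant or lipid-lowering medication.

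**The concern.** Take three patients at 1 year. The first took a statin for years before transplant and has not changed it. The second was untreated and started because triglycerides rose on the mTOR inhibitor. The third was never treated. On the literal rule the first two are both events, yet only the second says anything about the randomised drug. A prior user whose treatment had to be stepped up also scores the same as one who was stable.

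The medication rate therefore mixes use that predates randomisation with use that follows it. What is at stake is how readable this comparison is. The background section says the trial wants to characterise the side-effect profile of Zortress relative to Rapamune, and new need for lipid treatment is one way a difference would show. An all-users rate gives a smaller difference than the one caused by the drugs.

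**Working it through.** The plan states no figure for this outcome, so there is nothing to reproduce. The check is how far the literal rule shrinks a given difference.

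**Inputs from the documents.** Total size: "We would propose to enroll a total of 60 patients over 12 months" (section 5). Allocation: "We will randomize 2:1 Zortress to Sirolimus using a random number generator" (section 5), which gives 60 × 2/3 = 40 Zortress and 60 × 1/3 = 20 Rapamune.

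**Assumed, because the documents are silent.** Share b on lipid-lowering drugs before transplant: 10% to 70%. All prior users stay on treatment. New starts among untreated patients by 1 year: 30% Zortress, 60% Rapamune. Test: pooled chi-squared, two-sided 5%, all patients in the denominator.

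**Dilution.** With new-start rate p, the scored arm rate is b + (1 − b)p. The difference between arms is therefore (1 − b)(p_R − p_Z), whatever the start rates. Example at b = 20%: Zortress 0.20 + 0.80 × 0.30 = 0.44; Rapamune 0.20 + 0.80 × 0.60 = 0.68; difference 0.24 = 0.80 × 0.30.

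**Share of events that are prior users.** This is 60b / (40 × Zortress rate + 20 × Rapamune rate). At b = 20%: 12 / (17.6 + 13.6) = 38%.

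**Power.** Simulated with arms of 40 and 20, drawing baseline use and then new starts as binomials. The literal outcome (prior users plus starts, over all patients) is compared with new starts over untreated patients.

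| b | Scored rates, Z vs R | Difference (points) | Prior users among events | Power, as written | Power, new starts |
|---|---|---|---|---|---|
| 10% | 37% vs 64% | 27 | 22% | 0.53 | 0.58 |
| 20% | 44% vs 68% | 24 | 38% | 0.44 | 0.53 |
| 30% | 51% vs 72% | 21 | 52% | 0.35 | 0.48 |
| 50% | 65% vs 80% | 15 | 71% | 0.22 | 0.36 |
| 70% | 79% vs 88% | 9 | 85% | 0.11 | 0.25 |

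**Cross-check by normal approximation at b = 40%.** As written, rates are 0.58 and 0.76 and the pooled rate is 0.64. The null SE is √(0.64 × 0.36 × (1/20 + 1/40)) = 0.131, and the SE under the alternative is √(0.76 × 0.24/20 + 0.58 × 0.42/40) = 0.123. Power = Φ((0.18 − 1.96 × 0.131)/0.123) = 0.26. For new starts, with 24 and 12 untreated patients, the same formula gives 0.41.

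**Other start rates.** With 20% vs 50%, power as written is 0.35, 0.21 and 0.11 at b = 30%, 50% and 70%, against 0.53, 0.41 and 0.28 for new starts. With 30% vs 45%, neither version exceeds about 0.20 at any b from 10% to 70%.

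**No true difference.** With 30% new starts in both arms, both versions reject at about the nominal 5%.

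**Chance imbalance.** The SD of the difference in baseline use between arms is √(b(1 − b)(1/20 + 1/40)): 0.11 at b = 20% and 0.13 at 40% or 60%. A fraction (1 − p) of any such imbalance, 70% when p = 30%, carries into the observed difference.

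**The case against.** Prevalent use at 1 year is a legitimate randomised outcome, and preferring new starts is a choice of estimand. The test keeps its error rate, and chance imbalance in baseline use is ordinary sampling variation that the test already allows for. Every size above rests on an assumed baseline use and an assumed effect; at 10% to 20% use the loss is only 5 to 9 points of power. The protocol calls all its objectives exploratory and disclaims power, and neither version would be decisive. Section 3.2 names lipid panel results, especially triglycerides, and the scoring rule does not touch those. Requirement is undefined and could be scored as new requirement; nor do the documents state an all-patient denominator.

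Most of this stands, and it limits the point to a minor one. It does not remove it. The synopsis wording is use at 1 year, which is prevalence, and the authors wrote the restriction to new treatment for diabetes in the same sentence but not for lipids. Two analysts could score the same patient differently. Whatever the baseline share, the algebra moves the estimate towards no difference if prior users stay on treatment.

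A reader might go further and infer that the dilution helps the trial reach the conclusion it hopes for. The documents do not support that. The no-difference hypothesis in the synopsis follows the graft-loss, death, rejection and survival comparisons, and section 10.5 expects non-inferiority on the primary endpoint. On side effects, section 2 hopes that patients do better on everolimus, so dilution would work against that hope.

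**Conclusion.** The point holds as a minor one. As worded, the medication part of lipid control counts prior users as events. If they stay on treatment, a true difference in new need is multiplied by (1 − baseline use). That factor does not depend on the start rates; the power figures do, and they rest on an assumed 30% versus 60%. The loss is small at 10% to 20% baseline use and substantial at 30% to 70%.

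Two stronger statements are not supported. A reader might infer that the rate mainly reflects pre-transplant therapy; under these assumptions that is so from about 30% baseline use (52% of events), but not at 10% or 20%, and the documents do not say where this population lies. A reader might also infer that a treated patient can never respond to the study drug on this outcome; that needs prior users never to stop treatment, which is an assumption. The consequence is an attenuated and ambiguous estimate, not a false-positive risk, and the primary endpoint is not involved.

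**What to change.** In 10.1.2, 10.2.1 and the synopsis, define the medication part as the first start of lipid-lowering medication after transplant among patients not taking it at screening, compared between arms in that group. The group is fixed before randomisation, so the comparison stays randomised. If an all-patient use figure is kept, stratify it by baseline use (yes/no).

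Record baseline lipid-lowering use for every patient. The exclusion in 5.2 needs treatment status only for those above the cut-offs, and Table 7-1 has no medication row, so the field should be added explicitly. Intensification in prior users can be reported descriptively by arm, but this is optional because it needs agent and dose at baseline and follow-up.

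The cost is wording, one baseline field and a smaller denominator: about 30 patients (20 and 10) if half are treated at entry, or 18 (12 and 6) if 70% are.
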